## **11.2 Coordinating Site**

All reportable AEs/SAEs occurring at the coordinating site must be reported to TJU IRB/Medical Monitor using the On-site OHR-10 Form, and should comprise a full written summary detailing relevant aspects of the adverse events in question, including grading and attribution to study drug. Where applicable, information from relevant hospital case records and autopsy reports should be included.

Reportable AE/SAEs from TJU will then also be faxed to the Participating Site coordinator per same guidelines as outlined above.

All unexpected AE./SAEs that are probably or definitively related to the study procedures from either the participating site or the coordinating site must be reported to the TJU IRB within 48 hours of the TJU Principal Investigator being notified of the event.

Any on-study death (regardless of relationship) and any unforeseen death, that indicates that the participant or others may be at increased risk of harm, must be submitted to the TJU IRB/Medical Monitor within 24 hours of notification. Any unrelated SAE should be reported within 5 working days. The TJU study team will notify the TJU IRB appropriately.

Additional follow-up SAE reports should be submitted when available.

Unanticipated problems that pose risk to subjects or others, and that are not AEs/SAEs should be reported to TJU IRB within 10 working days using form OHR-20 and should be faxed to the Participating Site coordinator within 24 hours.

## **12 Study Oversight**

In addition to the PI's responsibility for oversight, study oversight will be under the direction of the SKCC's Data and Safety Monitoring Committee (DSMC). The DSMC operates in compliance with a Data and Safety Monitoring Plan (DSMP) that is approved by the Clinical Trials Oversight Committee (CTOC).

## **13 Clinical Site Monitoring and Auditing**

Clinical site monitoring and auditing is conducted to ensure that the rights of human participants are protected, that the study is implemented in accordance with the protocol and/or other operating procedures, and that the quality and integrity of study data and data collection methods are maintained. Monitoring and auditing for this study will be performed in accordance with the SKCC's Data and Safety Monitoring Plan (DSMP) developed by the SKCC Data and Safety Monitoring Committee (DSMC). The DSMP specifies the frequency of monitoring, monitoring procedures, the level of clinical site monitoring activities (e.g., the percentage of participant data to be reviewed), and the distribution of monitoring

reports. Some monitoring activities may be performed remotely, while others will take place at the study site(s). Appropriate staff will conduct monitoring activities and provide reports of the findings and associated action items in accordance with the details described in the DSMP.

The investigator will permit study-related monitoring, audits, and inspections by the IRB, the funding sponsor, government regulatory bodies, and University compliance and quality assurance groups of all study related documents (e.g. source documents, regulatory documents, data collection instruments, study data etc). The investigator will ensure the capability for inspections of applicable study-related facilities (e.g. pharmacy, diagnostic laboratory, etc).

Participation as an investigator in this study implies acceptance of potential inspection by government regulatory authorities and applicable University compliance and quality assurance offices.

Representatives from the Thomas Jefferson University study team will monitor on site at the participating site (or virtually if geographically impossible) within 4 weeks of the first subject enrolling, and every 4-6 weeks thereafter as outlined in the TJU Monitoring Policy. Additional study monitoring by an independent auditing agency will be conducted at 10% and 50% of site accrual per the TJU Data and Safety Monitoring Plan. This will either occur on-site, if feasible, or will require participating sites to send TJU all source documents, patient charts, etc to TJU for audit.

Teleconferences with the PIs, research nurses/coordinators, and regulatory staff will occur quarterly. This will be a forum to discuss study related issues including accrual, SAE/AEs experienced, study response, deviations/violations and study management issues. Minutes of these discussions will be taken to document the date of these meetings, the participants and the issues that were discussed. Copies of these minutes will be maintained in the Regulatory Binders at all participating sites.

## **14 STATISTICAL CONSIDERATION**

### **14.1 Primary Endpoint**

The primary study endpoint is PEPI score 0 as defined in Appendix B. These results will be retrieved from the routine pathology report. The PEPI score will be reported using descriptive statistics and 95% confidence intervals.

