## 2.0 RATIONALE

A phase II randomized study of neoadjuvant letrozole and everolimus vs. letrozole alone enrolled 270 postmenopausal patients with tumors larger than 2 cm, and showed improvements in clinical and radiographic responses [7]. However, this study did not select

patients by proliferation rate or recurrence score and thus likely included a broad mix of ER+ cancers. We propose a single arm phase II trial evaluating the combination of everolimus and an aromatase inhibitor in postmenopausal women with hormone receptor positive/HER2 negative breast cancers with low and intermediate risk ( $\leq 25$ ) Recurrence Scores by Oncotype Dx. The type of aromatase inhibitor administered during this trial will be at the physician's choice, since they all can be considered equivalent in activity based on the results of the ACOSOG Z1031 trial [1]. Our study eligibility will be limited to patients with 'low to moderately aggressive', hormone-responsive tumors, identified by recurrence score  $\leq 25$ , similar to the group of patients in whom the omission of adjuvant chemotherapy is being tested by the TAILORx and SWOG 1007 studies. Therefore, we propose to use pretreatment recurrence score to identify patients most likely to benefit from neoadjuvant endocrine therapy, and determine if the addition of the mTOR inhibitor everolimus enhances that response.

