Our primary endpoint will be to evaluate response defined as a PEPI -0. Results from ACOSOG Z1031 demonstrated no difference in clinical response or surgical outcomes between luminal A vs luminal B tumors in postmenopausal patients treated with three different aromatase inhibitors, however, there were significantly higher responses defined by a Preoperative Endocrine Prognostic Index (PEPI) score of 0 in luminal A vs luminal B tumors (27.1% v 10.7 %; P=.0004) [1]. A PEPI score 0 was also highest in tumors with Ki67 levels  $<10\%$  at baseline. Kelly et al compared risk assignment by PAM 50 Breast cancer intrinsic classifier and Oncotype DX recurrence score in 151 hormone receptor positive stage I-II breast cancers [2]. The majority (83%) of low recurrence score cases were found to be luminal A subtype by PAM 50. Additionally, half of the intermediate recurrence scores were re-categorized as low risk luminal A subtypes by PAM 50. While there are no available reports of the incidence of PEPI-0 following neoadjuvant AI therapy in hormone receptor positive breast cancer patients with an Oncotype of  $\leq 25$ , Ellis et al did report a PEPI-0 of 27% in the Luminal A subset in ACOSOG Z1031. Therefore this will be used as our benchmark. Patients with clinical stage I –III (just like ACOSOG Z1031) hormone receptor tumors and RS  $<25$  will be eligible for the study.

An ongoing large randomized phase III clinical trial (SWOG 1007) is designed to evaluate the benefit from chemotherapy for ER positive breast cancer with 1-3 positive lymph nodes and an Oncotype Dx recurrence score of  $\leq 25$  (low-intermediate recurrence scores). It is likely that this tumor subset is more sensitive to a combination of an mTOR inhibitor and endocrine therapy. Our proposed neoadjuvant trial will provide rapid and complementary information to assess whether everolimus might improve the efficacy of endocrine therapy in breast cancers with low to intermediate recurrence scores.

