### 3.0 STUDY OBJECTIVES

#### Primary objectives:

- The primary objective of the study is to determine the percent of postmenopausal patients with stage II-III hormone receptor positive/ HER2 negative breast cancer and an Oncotype Dx recurrence score  $\leq 25$  who achieve a PEPI score of 0 following neoadjuvant treatment with everolimus and an aromatase inhibitor

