### **14.2 Secondary Endpoint**

1. Clinical and radiographic response rate will be assessed by two measures. Radiographic tumor size measurements by MRI (or ultrasound when MRI not feasible) and physical examination after completion of all chemotherapy compared to baseline. Response will be categorized following RECIST criteria (Appendix A). The results will be reported as descriptive statistics with 95% confidence intervals.

2. Toxicity will be recorded using the standard NCI Common Toxicity Criteria as per <http://ctep.cancer.gov/forms/CTCAEv4.pdf>. Results will be reported in a tabular format by worst grade and occurrence per patient over the entire study period
3. Measurements of Ki67 at baseline and after completion of neoadjuvant therapy.
4. Baseline and residual cancer tissue will be collected for future biomarker analysis. Considering the small sample size of the study the biomarker results will be exploratory and hypothesis generating. The planned molecular analysis of these tissues may include gene expression profiling, and PI3K pathway markers.

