### **14.3 Sample Size calculation**

This is a single arm phase II study to evaluate neoadjuvant endocrine therapy with everolimus in postmenopausal women with ER+/HER2 – breast cancers with low and intermediate risk ( $\leq 25$ ) Recurrence Scores. The primary endpoint will be response defined as a PEPI-0 rate. A treatment with minimal activity would be expected to have PEPI-0 rate of 25%. Alternatively, a treatment will be considered worthy of further study if its true PEPI-0 rate is 45% or better.

Simon's optimal two-stage design is employed for this single-arm phase II trial and a total of 27 eligible patients will be enrolled. First, 15 eligible patients will be enrolled in the study. If 5 or more of 15 eligible patients achieve a PEPI score of 0, we will enroll another 12 patients into the study. If 10 or more of the 27 eligible patients achieve a PEPI score of 0, we will conclude that the regimen warrants further study. This design has a power of 80% and a one-sided significance level of 0.1. The probability of stopping early if the treatment is ineffective (true PEPI-0 rate of  $\leq 25\%$ ) is 69%. Assuming that 10-20% of enrolled patients will be invaluable, we plan to enroll up to 33 in total.

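### Does leaving the method for the 95% interval on the PEPI-0 rate unnamed leave the primary result open to choice?

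*Combined protocol and SAP*

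**What the plan says.** Section 3.0 states an estimation objective: "The primary objective of the study is to determine the percent of postmenopausal patients" who reach PEPI 0. Section 14.1 gives the planned reporting in one sentence: "The PEPI score will be reported using descriptive statistics and 95% confidence intervals". Section 14.2 treats the clinical and radiographic response rates the same way: "The results will be reported as descriptive statistics with 95% confidence intervals". Neither section names an interval method or refers to the two-stage design.

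The decision rule is in section 14.3. The low-activity rate is 25%, and for the target rate the section says "Alternatively, a treatment will be considered worthy of further study if its true PEPI-0 rate is 45% or better". The stage-1 rule is "If 5 or more of 15 eligible patients achieve a PEPI score of 0, we will enroll another 12 patients into the study". The final rule is "If 10 or more of the 27 eligible patients achieve a PEPI score of 0, we will conclude that the regimen warrants further study".

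Section 2.0 gives a third figure. It notes that an earlier aromatase-inhibitor trial did "report a PEPI-0 of 27% in the Luminal A subset in ACOSOG Z1031. Therefore this will be used as our benchmark". The same section says the trial should "determine if the addition of the mTOR inhibitor everolimus enhances that response".

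**The concern.** The primary objective is to estimate a rate, and section 2.0 names 27% as the yardstick. The rule in section 14.3 is built on 25%, so the estimate and interval from section 14.1 are the only planned figures that can be set beside 27%. With 27 patients the binomial methods differ by about two percentage points at the lower limit, enough to put 27% inside or outside the interval at a plausible result.

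If the method is picked after the count is known, it could be picked for the reading it gives. A second worry is nominal coverage. The wording would permit a Wald interval, which at these sample sizes covers less than its 95% label. A third is that an ordinary binomial interval ignores the chance of stopping after 15 patients.

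**Working it through.** **Inputs.** From section 14.3: stage 1 n = 15, continue at 5 or more; total n = 27, success at 10 or more; null rate 25%; target rate 45%. From section 2.0: benchmark 27%. From section 14.1: 95% level. The plan names no method, so the candidates below are assumptions.

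**1. The plan's own figures.** Let X1 be the stage-1 count (15 patients) and X2 the stage-2 count (12 patients).
- Early stopping at 25%: P(X1 ≤ 4) = 0.6865 (stated: 69%).
- P(success | p) = Σ over x1 = 5 to 15 of P(X1 = x1) × P(X2 ≥ 10 − x1). This is 0.0973 at p = 0.25 (stated: 0.1) and 0.8012 at p = 0.45 (stated: 80%).

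The stated design reproduces. No interval enters these formulas.

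**2. Limits at 12/27 (estimate 0.4444).**
- Wald: 0.4444 ± 1.96 × √(0.4444 × 0.5556 / 27) = 0.4444 ± 1.96 × 0.0956 = 0.257 to 0.632.
- Wilson: centre (0.4444 + 3.8415/54) / (1 + 3.8415/27) = 0.5156/1.1423 = 0.4514. Half-width 1.96 × √(0.009145 + 0.001317) / 1.1423 = 0.1755. Interval 0.276 to 0.627.
- Clopper-Pearson: lower limit is the 2.5% point of Beta(12, 16), 0.2548; upper limit is the 97.5% point of Beta(13, 15), 0.6467.
- Two-stage exact lower limit: the p solving Σ over x1 = 5 to 15 of P(X1 = x1) × P(X2 ≥ 12 − x1) = 0.025, which is 0.2559.

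All four lower limits exceed 25%. Only Wilson exceeds 27%. Of the other common choices, Agresti-Coull (27.6%) and Jeffreys (27.06%) also exceed 27%, while mid-P (26.75%) does not. Jeffreys would fail against the unrounded 27.1% given in section 2.0.

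**3. Every possible outcome.** I applied the Clopper-Pearson, Wald and Wilson formulas to all final results (0 to 4 of 15, and 5 to 27 of 27) and compared each interval with 25%, 27% and 45%. They disagree at four results:

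| Result | Clopper-Pearson | Wald | Wilson | Disagreement | Probability at 25% / 45% | Decision under 14.3 |
|---|---|---|---|---|---|---|
| 1/15 | 0.2–31.9% | −6.0–19.3% | 1.2–29.8% | only Wald excludes 25% and 27% | 6.7% / 0.2% | stop |
| 3/15 | 4.3–48.1% | −0.2–40.2% | 7.0–45.2% | only Wald excludes 45% | 22.5% / 3.2% | stop |
| 7/27 | 11.1–46.3% | 9.4–42.5% | 13.2–44.7% | only Clopper-Pearson includes 45% | 5.1% / 0.6% | not a success |
| 12/27 | 25.5–64.7% | 25.7–63.2% | 27.6–62.7% | only Wilson excludes 27% | 1.3% / 14.6% | success |

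At 11/27 all three include 27% (lower limits 22.4%, 22.2%, 24.5%). At 13/27 all three exclude it (28.7%, 29.3%, 30.7%). Against 25% they agree at every count that meets the 10/27 rule.

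**4. Is the interval a decision tool here?** At 10/27 the lower limits are 19.4%, 18.8% and 21.5%, so each interval includes 25%, and section 14.3 still declares success. The same holds at 11/27. Whether a 95% interval excludes a reference rate is therefore not the plan's criterion, even against its own null.

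**5. Coverage under the two-stage design, true rates 25% to 45%.**
- Two-stage exact: minimum 95.0%, mean 97.2%.
- Clopper-Pearson: minimum 95.5%, mean 97.2%.
- Wilson: minimum 92.6%, mean 95.4%.
- Wald: minimum 86.6% (at a true 30.55%), mean 91.4%.

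**6. Effect of ignoring the stage-1 stop.** At 10/27 Clopper-Pearson gives 19.4–57.6% and the two-stage exact interval 19.9–58.9%. Over true rates of 10% to 70%, Clopper-Pearson coverage falls no lower than 94.2%, near a true 57.7%.

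**The case for a change.** The case for a change is that naming a method costs one sentence and removes a choice that could otherwise be made after the count is seen. Section 2.0 calls 27% the benchmark, so readers will compare the interval with it whether or not section 14.1 invites them to. And 12/27 is the modal result if the regimen performs as hoped.

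The facts in this argument stand: no method is named, the split at 12/27 is real, and a Wald interval labelled 95% would be poor. The weight given to them does not.
- The test of whether the interval excludes 27% appears nowhere in the plan. Section 14.1 asks for description, and section 14.3 sets the formal low-activity rate at 25%.
- The benchmark is itself an estimate from a subset of another trial. A lower limit of 27.6% rather than 25.5% is weak ground for reading the same 12 responders differently.
- Modal does not mean probable. At a true 45% the chance of some result other than 12/27 is 1 − 0.146 = 85.4%. The probability of 12/27 falls to 8.8% at a true 35% and 4.2% at 30%.
- The splits at 1/15 and 3/15 come only from Wald, and at those counts the trial has already stopped. At 7/27 it has already missed its threshold.

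**Conclusion.** No change to the plan is needed. Leaving a routine binomial interval unnamed in a 27-patient single-arm trial is a gap in detail that an analyst fills sensibly. Clopper-Pearson and the two-stage exact interval hold at least 95% coverage across the null-to-target range, and Wilson averages 95.4%. Each gives a sound description of the PEPI-0 rate and the same conclusion under section 14.3.

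What remains is presentational: among results that meet the success rule, one count (12/27, probability 14.6% at a true 45%) at which the lower limit falls on one side or the other of 27%. The go/no-go decision, alpha, power and patient numbers do not move.

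This rests on three assumptions: the denominators are exactly 15 and 27 eligible patients, as section 14.3 states; the analyst uses a standard method other than Wald; and the interval is read as section 14.1 presents it, as description. With other denominators the count at which methods split would shift, but the decision would still rest on counts.

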### **14.2 Secondary Endpoint**

1. Clinical and radiographic response rate will be assessed by two measures. Radiographic tumor size measurements by MRI (or ultrasound when MRI not feasible) and physical examination after completion of all chemotherapy compared to baseline. Response will be categorized following RECIST criteria (Appendix A). The results will be reported as descriptive statistics with 95% confidence intervals.

2. Toxicity will be recorded using the standard NCI Common Toxicity Criteria as per <http://ctep.cancer.gov/forms/CTCAEv4.pdf>. Results will be reported in a tabular format by worst grade and occurrence per patient over the entire study period
3. Measurements of Ki67 at baseline and after completion of neoadjuvant therapy.
4. Baseline and residual cancer tissue will be collected for future biomarker analysis. Considering the small sample size of the study the biomarker results will be exploratory and hypothesis generating. The planned molecular analysis of these tissues may include gene expression profiling, and PI3K pathway markers.

### **14.3 Sample Size calculation**

This is a single arm phase II study to evaluate neoadjuvant endocrine therapy with everolimus in postmenopausal women with ER+/HER2 – breast cancers with low and intermediate risk ( $\leq 25$ ) Recurrence Scores. The primary endpoint will be response defined as a PEPI-0 rate. A treatment with minimal activity would be expected to have PEPI-0 rate of 25%. Alternatively, a treatment will be considered worthy of further study if its true PEPI-0 rate is 45% or better.

Simon's optimal two-stage design is employed for this single-arm phase II trial and a total of 27 eligible patients will be enrolled. First, 15 eligible patients will be enrolled in the study. If 5 or more of 15 eligible patients achieve a PEPI score of 0, we will enroll another 12 patients into the study. If 10 or more of the 27 eligible patients achieve a PEPI score of 0, we will conclude that the regimen warrants further study. This design has a power of 80% and a one-sided significance level of 0.1. The probability of stopping early if the treatment is ineffective (true PEPI-0 rate of  $\leq 25\%$ ) is 69%. Assuming that 10-20% of enrolled patients will be invaluable, we plan to enroll up to 33 in total.

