	
10. Patients must not have a known diagnosis of hepatitis B or C. Patients with the following risk factors must have hepatitis screening pre-treatment:
 

• Blood transfusions prior to 1990

• Current or prior IV drug users

• Current or prior dialysis

• Household contact with a hepatitis B or C patient

• Current or prior high-risk sexual activity

• History of jaundice.

 
11. Patients must not have any known uncontrolled underlying pulmonary disease or severely impaired lung function (spirometry and DLCO 50% or less of normal and O2 saturation 88% or less at rest on room air),
 
12. Active (acute or chronic) or uncontrolled severe infection.
 
13. Patients who have received live attenuated vaccines within 1 week of start of Everolimus, or have plans to receive such vaccination while on protocol treatment. Patient should also avoid close contact with others who have received live attenuated vaccines. Examples of live attenuated vaccines include intranasal influenza, measles, mumps, rubella, oral polio, BCG, yellow fever, varicella and TY21a typhoid vaccines;
 
14. , Patients who are currently part of or have participated in any clinical investigation with an investigational drug within 1 month prior to dosing;
 
15. Patients must not have taken within 14 days prior to registration , be taking, nor plan to take while on protocol treatment, strong CYP3A4 inhibitors, and/or CYP3A4 inducers.
 
16. Patients with active bleeding diathesis.

Statistical Methodology:	This is a single arm phase II study to evaluate neoadjuvant endocrine therapy with everolimus in postmenopausal women with hormone receptor positive/HER2 negative breast cancers with low and intermediate risk ( $\leq 25$ ) Oncotype Dx recurrence score. The primary endpoint is response defined as a PEPI-0 rate. A treatment with minimal activity would be expected to have PEPI-0 rate of 25%. Alternatively, a treatment will be considered worthy of further study if its true PEPI-0 rate is 45% or better. Simon's optimal two-stage design is employed for this single-arm phase II trial. The sample size is 27. Assuming 10-20% ineligibility rate, we plan to enroll up to 33 patients totally.

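### The cap of 33 enrolled covers losses up to 18%, not the full 10-20% stated, if 27 eligible patients are to be kept

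*Combined protocol and SAP*

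**What the plan says.** Section 14.3 sets the target: "Simon's optimal two-stage design is employed for this single-arm phase II trial and a total of 27 eligible patients will be enrolled". The interim rule is "If 5 or more of 15 eligible patients achieve a PEPI score of 0, we will enroll another 12 patients into the study", and the final rule is "If 10 or more of the 27 eligible patients achieve a PEPI score of 0, we will conclude that the regimen warrants further study". The operating characteristics follow: "This design has a power of 80% and a one-sided significance level of 0.1". The section then sets the enrolment ceiling: "Assuming that 10-20% of enrolled patients will be invaluable, we plan to enroll up to 33 in total".

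The Statistical Methodology row of the synopsis repeats the range and the ceiling but calls the loss ineligibility: "Assuming 10-20% ineligibility rate, we plan to enroll up to 33 patients totally". Section 4.0 gives the same 27 and 33 but assumes a single loss rate of 10%. No section gives a final decision rule for fewer than 27 eligible patients.

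**The concern.** Two places present 33 as enough to keep 27 eligible patients after a loss of anywhere from 10% to 20%. At the upper end it is not enough. The division is the same whether the loss means ineligible or inevaluable patients.

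The effect falls on the final analysis. The design meets its 80% with almost nothing to spare, so any shortfall below 27 with the cut-off of 10 unchanged takes power under the stated figure. The team would then have to apply a rule written for 27 to a smaller number, or choose a new cut-off after the data are in.

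**Working it through.** **Inputs.** All are from section 14.3: null rate 25%, alternative rate 45%, continue if at least 5 of 15, positive if at least 10 of 27, loss 10-20%, cap 33. Section 4.0 gives a 10% loss with the same cap.

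**1. Reproduce the printed design.** With X1 ~ Bin(15, p) and X2 ~ Bin(12, p), the probability of a positive trial is the sum over x from 5 to 15 of P(X1 = x) × P(X2 ≥ 10 − x).

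- p = 0.45: power 0.801
- p = 0.25: type I error 0.097
- Early stopping, P(X1 ≤ 4): 0.686 at p = 0.25 and 0.120 at p = 0.45

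A full search returns these sizes and cut-offs as Simon's optimal design. The printed 80%, 0.1 and 69% all stand.

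**2. Check the cap.** The number to enrol for an expected 27 is 27/(1 − d), where d is the loss rate.

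- d = 0.10: 27/0.90 = 30, so 33 is ample
- d = 0.15: 27/0.85 = 31.8, so 32, and 33 is enough
- d = 0.20: 27/0.80 = 33.75, so 34, and 33 is one short

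In the other direction, 33 × 0.80 = 26.4, and the most that 33 can lose while keeping 27 is 6/33 = 18.2%.

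**3. Chance of reaching 27.** If losses are independent, the number of usable patients among 33 is M ~ Bin(33, 1 − d). This applies to a trial that passes stage 1 and enrols to the cap.

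**4. Power by the number obtained.** Keep the cut-offs of 5 of 15 and 10 in total, and replace the 12 in step 1 by m − 15:

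| Eligible patients m | Power at 45% | Type I error at 25% |
|---|---|---|
| 27 | 80.1% | 0.097 |
| 26 | 77.2% | 0.081 |
| 25 | 73.4% | 0.066 |
| 24 | 68.6% | 0.052 |

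Lowering the cut-off to 9 at m = 26 gives power 83.7% but type I error 0.146, so moving the cut-off does not restore both error rates.

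**5. Average over the number obtained.** Average power is the sum over m of P(M = m) × power(min(m, 27)):

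| Loss rate | P(at least 27 of 33) | Average power | Average type I error |
|---|---|---|---|
| 10% | 95.8% | 79.9% | 0.096 |
| 15% | 78.3% | 78.6% | 0.091 |
| 20% | 50.0% | 75.2% | 0.079 |

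At 20% loss, the chance of 25 or fewer is 33% and of 24 or fewer is 20%.

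**6. Would a cap of 34 cure it?** At 20% loss, 34 enrolled gives P(at least 27) = 63.3% and average power 76.9%. A cap of 38 gives 93.8% and 79.7%.

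**The case against.** The strongest reply is that the gap is one patient at one end of an approximate range. In expectation it is 27 − 26.4 = 0.6 of a patient. At 10%, the only rate that section 4.0 gives, the cap is comfortable, and at 15% the power loss is under 2 points. This stands, and it limits the priority.

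A second reply is that most of the power loss at 20% comes from random variation in the number of losses and not from the division. Power falls by 80.1 − 75.2 = 4.9 points, and a correctly divided cap of 34 recovers only 76.9 − 75.2 = 1.7 of them. This also stands. The 50% figure therefore should not be read as the price of an arithmetic slip. A reader might infer that 33 came from multiplying (27 × 1.20 = 32.4, rounded up), but the documents do not show how it was derived, and the shortfall does not depend on it.

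A third reply is that the error is conservative, because type I error falls to about 0.08. That is true, but the cost is power. The lack of a rule for fewer than 27 is a separate gap that would exist at any cap.

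None of this rescues the sentence as printed. It links 33 to losses up to 20%, and 33 does not cover 20%.

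**Conclusion.** The enrolment statement in section 14.3 and the synopsis is wrong at its upper end: 33 allows for up to 6 losses (18.2%), not 20%. At 20% loss, overall power averages about 75% with type I error about 0.08, and a trial that continues to stage 2 has about an even chance of reaching 27. At 15% power is about 79%, and at 10% the cap is adequate.

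The power figures assume independent losses, lost patients excluded and replaced up to the cap, the cut-offs of 5 of 15 and 10 in total kept, and 15 evaluable patients at stage 1.

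Three stronger readings are not supported:

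- A reader might infer that the stated 80% power is wrong. Section 14.3 states it for 27 eligible patients, and there it is right.
- A reader might infer that half of all such trials would end short of 27 because of the cap. The 50% applies only after stage 1 is passed. The design stops at 15 with probability 69% at a true rate of 25% and 12% at 45%.
- A reader might count lost patients as non-responders among 27, which would put power at about 48% at 20% loss (0.45 × 0.80 = 0.36). The rules in section 14.3 count eligible patients, and enrolling beyond 27 makes sense only if losses are replaced.

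Priority is low to moderate.

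**What to change.** Keep the cap at 33 and restate what it covers. In section 14.3 and the synopsis, write: *Up to 33 patients will be enrolled, which allows for up to 6 losses (18%). The 80% power applies if 27 eligible patients are obtained; at a 20% loss rate about 26 are expected and average power is about 75%.* State beside it the assumptions behind the 75%.

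Reconcile the 10% in section 4.0 with the 10-20% in section 14.3 and the synopsis, so that one loss assumption goes with the one cap.

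Printing 34 is not a remedy, because at 20% loss it gives only a 63% chance of 27 and power of about 77%. It would also mean changing the number wherever 33 appears.

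The cost is a sentence or two in each of two places and one aligned figure in section 4.0. The design and the cut-offs do not change. The only downside is a slightly less favourable stated figure.
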